6.2.4 Subgroup analyses

Descriptive statistics for the primary and the first three secondary efficacy variables will be reported separately for each region/country (the US, Japan, other countries), race and ethnicity for the FAS population.

6.3 Pharmacokinetics/pharmacodynamics

The planned analysis of pharmacokinetic and pharmacodynamics data will be described in a separate M&S Analysis Plan and results will be reported in a separate M&S Report.

6.4 Safety

The safety variables will include the following secondary and other safety variables:

The secondary safety variables are:

- Endometrial histology (e. g., benign endometrium, presence or absence of hyperplasia or malignancy)
- Endometrial thickness

The other safety variables are:

- Endometrial histology (diagnosis of Progesterone receptor modulator-associated changes (PAEC), individual features of PAEC)
- Ovarian cysts (number, size)
- Laboratory parameters
- AEs
- Cervical smear
- Vital signs
- Percentage of subjects with hemoglobin $\leq 10.9 \text{ g/ dL}$
- Findings resulting from liver monitoring
- Findings resulting from adrenal monitoring
- Findings resulting from skin monitoring
- UF-DBD bleeding pattern per 28 days and 84 days

All safety analyses are descriptive, and variables will be summarized by descriptive statistics as appropriate. All safety analyses are done for the actual treatment (as-treated) and performed on the SAF.

In contrast to the derivation of efficacy variables, even if an endometrial biopsy was conducted, bleeding and 'spotting' reported on such days will also be used when deriving safety variables.

No results for the pooled treatment group A1+B2 will be presented, if not specified otherwise.

Pregnancy test results based on ultrasound and urine pregnancy test will be reported by treatment group and visit. Ultrasound is performed as confirmation after positive urine pregnancy test.

6.4.1 Secondary safety variables

6.4.1.1 Endometrial histology

For endometrial histology evaluations (e.g., benign endometrium, presence or absence of hyperplasia or malignancy) the following time intervals / time points will be considered:

• Any time point

- Intervals A (acc to Figure 4–1)
- Intervals B (acc to Figure 4–1)
- "Exit examination" intervals
- Bleeding episode after last treatment period time windows in subjects with at least 56 days of treatment within the treatment period (by TP1, TP2 and overall):
 - From start of the patients' last treatment period until Day 55 of the same treatment period
 - From Day 56 of the same treatment period until the last day of the 1st bleeding episode after the treatment period
 - After 1st bleeding episode of the same treatment period, i.e., from 1st day after the end of the 1st bleeding episode to the last day of the 2nd bleeding episode
 - After 2nd bleeding episode of the same treatment period, i.e., from 1st day after the end of the 2nd bleeding episode to the last day of the 3rd bleeding episode
 - After 3rd bleeding episode of the same treatment period, i.e., from 1st day after the end of the 3rd bleeding episode to the last day of the 4th bleeding episode

Analyses will present the number and percentage of either subjects or biopsies. A subgroup analysis by exposure group (i.e., treatment duration \leq 90 days, 91 to 180 days, etc.) will be presented for endometrial biopsy main results.

Presentations will be done for

- the Safety read (Reader #1 or #5)
- the Majority read (Reader #2 #4)
- All reads (Reader #1 #5)

Safety read: For the safety read only one result will be available per biopsy (based on either Reader #1 or #5), whereas for the "majority read" and "all reads" more than one reader result needs to be considered.

Majority read: Majority read results will only be provided in case biopsy data from Readers #2, #3 and #4 are available. Majority read will be determined for main results and subcategories (see Table 6–1). First, adequacy (for part II and III) or sufficiency (for part IV) of tissue will be investigated by all readers. If at least 2 of the 3 readers consider the tissue adequate/sufficient, the majority for the main results will be assessed. If there is a majority with respect to the main result, majority of the respective subcategories will be determined. If no majority result is available (3 different results in 3 readers, 2 different results in 2 readers), either "no consensus" or the worst case will be presented. Table 6–1 presents an overview of the biopsy results including the approach which is used in case no majority is available.

For subcategories where multiple selections are possible, an individual feature will be considered a majority read result if at least 2 readers have ticked this feature. That means that more than just one subcategory can be a majority read result for a biopsy.

All read: All read results will be based on all biopsies with results from at least one reader. A biopsy is considered non-benign in case "Benign endometrium" = "No" or "Endometrial Hyperplasia (WHO 2014)" or "Endometrial Hyperplasia (WHO 1994)" or "Malignant Neoplasm" = "Yes".

Multiple biopsies per time interval/time point: For the exit examination the last available measurement will be used if there are several measurements. For any other time intervals / time points, the analyses in which numbers of subjects are reported will be based on a 'worst case approach'. In this approach, the worst measurement within each of the above-mentioned time intervals / time points will be used. These worst outcomes across time intervals / time points are determined for each endpoint in Table 6–1.

Table 6–1: Overview of biopsy endpoints including majority result handling and worst case

Part		Endpoint	No majority available	Worst case across time intervals for subject- based analyses
		Main results		
1		Adequate endometrial tissue	- (not possible)	"Yes"
II	Main diagnosis	Benign endometrium Endometrial Hyperplasia (WHO 2014) Malignant Neoplasm	Worst case: List is ordered by severity, from low to high	List is ordered by severity, from low to high
Ш	1	Endometrial Polyp	Worst case: yes	"Yes"
IV		Tissue sufficient for PAEC read	- (not possible)	"Yes"
	PAEC	PAEC present	Worst case: yes	"Yes"
		Subcategories		
II	s	Benign endometrium (select one) Atrophic Inactive Proliferative Disordered Proliferative Secretory including progestin and OCP effect Menstrual Endometritis Other, specify	"no consensus"	- (will not be presented)
	Main diagnosis	Endometrial Hyperplasia (WHO 2014) (select one) Hyperplasia without atypia Atypical hyperplasia / Endometrioid Intraepithelial Neoplasia (EIN)	Worst case: Atypical hyperplasia / Endometrioid Intraepithelial Neoplasia (EIN)	Atypical hyperplasia / Endometrioid Intraepithelial Neoplasia (EIN)
Ш		Endometrial Polyp (select one)	"no consensus"	- (will not be presented)
IV	PAEC	PAEC (tick all that apply) Pre-Decidua Absent Extensive cysts Present Secretory Changes, Extensive Mitoses (required, may be rare) Apoptosis Abnormal Vessels	"no consensus"	- (will not be presented)

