h. Only to be performed in subjects who did not have a post-treatment endometrial biopsy (defined as biopsy taken at the earliest 7 days before last study drug intake) with a normal result. For subjects with menstrual cycles the endometrial biopsy should be taken between Day 7 to 15 (inclusive) of a menstrual cycle. This is defined as diagnosis of safety read and of all 3 individual components of the multiread to be “benign endometrium” in Part II of the evaluation form. In addition, the majority diagnosis needs to be “PAEC no” in Part IV of the evaluation form. Furthermore, an endometrial biopsy may also be triggered by results of ultrasound examination or bleeding data (see Section 9.6.3.2.7). The biopsy CRF page needs to be completed for all subjects, including cases where according to protocol no biopsy is required.  
i. In subjects who take biotin, the last dose of biotin should be at least 72 hours prior to hormone testing.

AE = adverse event, MRI = magnetic resonance imaging, PAEC = progesterone receptor modulator-associated endometrial changes

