  - A robust adrenal safety monitoring program has been implemented in all ongoing vilaprisan studies, including MRI of the adrenal glands, laboratory parameters, and evaluation of signs and symptoms indicative of adrenal disorder. A systematic approach of assessment and evaluation of adrenal gland findings will be applied as described in Section 9.6.3.8. Any adrenal abnormality assessed as relevant by either the adrenal gland expert or the local specialist will need to be documented as an AESI and to be reported to the sponsor’s pharmacovigilance department following the same standard process (reporting timelines, AE CRF and AE complementary pages) as serious AE. Tumors of the adrenal glands (diagnosed by the MRI central read, the adrenal gland expert or the local specialist) should in addition be reported as SAEs to ensure timely reporting to regulatory agencies.

Progesterone receptor modulator-associated endometrial changes (PAEC) will be assessed and documented in a systematic way (see Section 9.6.3.2.6). The results of the PAEC assessment will only be reported back to the investigators if they trigger the request for a repeat biopsy. Apart from cases where such a repeat biopsy is necessary, no clinical action for an individual subject is required based on the PAEC assessment results. PAEC assessment results are systematically collected for all samples and will be reported in aggregated form at the end of the study. They should therefore not be reported as AE for an individual subject.

A systematic approach of assessment and evaluation will also be applied to HMB (see Section 9.7.3), endometrial hyperplasia and endometrial thickening (see Sections 9.7.2 and 9.7.4), and liver parameters.

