### **9.6.3.2.6 Follow-up of PAEC**

Besides standard criteria (i.e., proliferative/secretory/atrophic endometrium, endometrial hyperplasia) presence of PAEC will be analyzed in all endometrial biopsy samples as part of the multi-reader assessment. The diagnosis of PAEC is based on a constellation of histologic features that, taken together, are characteristic. None of the features is unique, and to some extent any may be seen in subjects who have not been treated with PRMs. The common histologic features are endometrial glands showing cystic dilatation and an irregular architecture lined by inactive gland cells and compact, nondecidualized stroma.

If PAECs have been detected in the biopsy at the last visit before leaving the study according to the majority diagnosis resulting from the multi-reader assessment, the site will be informed and an additional biopsy should be scheduled. In case PAEC findings are still present, the study site will be informed and an additional biopsy is to be taken to evaluate resolution, with the timepoint of this additional biopsy to be determined case-by-case. If needed, more than one repeated biopsy may be taken and analyzed, except for cases with PAEC already present in the pre-treatment biopsy.

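### In the follow-up, any-time-point and exit tables of endometrial histology, how often a woman is biopsied depends partly on PAEC, and no planned table fixes the number of looks per woman.

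*SAP*

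**What the plan says.** **When a woman is biopsied again.** Protocol Table 9–1, footnote h, limits the closeout biopsy: "Only to be performed in subjects who did not have a post-treatment endometrial biopsy" with a normal result. Normal means a benign diagnosis from the safety reader and from all three panel readers, and in addition "the majority diagnosis needs to be “PAEC no” in Part IV of the evaluation form". The footnote and Section 9.6.3.2.2 also allow a biopsy for ultrasound or bleeding abnormalities.

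Section 9.6.3.2.6 adds repeats. "If PAECs have been detected in the biopsy at the last visit before leaving the study according to the majority diagnosis", then "the site will be informed and an additional biopsy should be scheduled". It continues: "If needed, more than one repeated biopsy may be taken and analyzed, except for cases with PAEC already present in the pre-treatment biopsy". Section 9.6.1.6 confines this to the end of a woman's participation: "The results of the PAEC assessment will only be reported back to the investigators if they trigger the request for a repeat biopsy".

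**How the biopsies are summarised.** SAP 6.4.1.1 covers any time point, Intervals A, Intervals B, the exit examination, and windows set by successive bleeding episodes after the last treatment period. Results may be counted by subject or by biopsy, for the safety read, the majority read and all reads. For subject counts outside exit: "In this approach, the worst measurement within each of the above-mentioned time intervals / time points will be used". For exit: "For the exit examination the last available measurement will be used if there are several measurements". SAP 6.4 makes all safety analyses descriptive.

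**The concern.** Under a worst-of-several rule, a woman with more biopsies has more chances of a bad score. If the number of biopsies were unrelated to treatment, this would only add noise. Here it depends partly on PAEC, a change named after the drug class under test. A difference between groups in hyperplasia, malignancy or polyp scores could then come partly from how often women were looked at.

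The exit rule works the other way. Biopsies are repeated to see whether PAEC has resolved, and hyperplasia may be followed until a benign result. The last value therefore shows the state after follow-up, not the frequency at the first post-treatment look.

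Endometrial histology is the first-listed secondary safety variable. The closeout programme exists partly because endometrial adenocarcinomas were seen in rodents. With few events expected, one or two scores found only on repeat biopsies would be hard to interpret.

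**Working it through.** The plan states no figure to reproduce, so the check traces the path from trigger to table and then illustrates the size.

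**Which tables are exposed**

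- *Treatment phase (Intervals A), and TP1 plus break or TP2 (Intervals B):* not by this route. PAEC is acted on only at the last biopsy and is not fed back earlier.
- *Follow-up phase and any time point:* yes. SAP 4.5 runs the follow-up phase to the last visit, so closeout and repeat biopsies can fall in the scored window.
- *PAEC itself under the worst-case rule:* not inflated. The triggering biopsy already scores Yes.
- *Non-benign diagnosis and polyp under the worst-case rule:* exposed. The triggering biopsy may be benign, so each repeat is a new chance.
- *Exit:* exposed in the opposite direction.
- *Bleeding-episode windows:* partly protected, because they align biopsies by time since treatment. They need at least 56 treatment days, stop at the fourth bleeding episode and rely on diary-defined episodes. Diary entry ended with Amendment 5, so late closeout or repeat biopsies are not clearly covered.

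**Worst-case rule: assumptions.** Let *q* be the chance of a non-benign score per biopsy, equal in all women (no true drug effect), with independent looks. Let *s* be the share of women with PAEC, *b* the base looks and *e* the extra looks triggered by PAEC. Then

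P = (1 − s)·[1 − (1 − q)^b] + s·[1 − (1 − q)^(b+e)].

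The values of *q*, *s*, *b* and *e* are all assumed.

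*Any reader non-benign.* Four reads per biopsy (one safety, three panel) at an assumed 0.5% each give q = 1 − 0.995^4 = 1.985%. With b = 1:

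| PAEC, higher vs lower group | e | P, higher | P, lower | Ratio | Excess per 52 women |
|---|---|---|---|---|---|
| 5% vs 1% | 1 | 2.08% | 2.00% | 1.04 | 0.04 |
| 20% vs 2% | 1 | 2.37% | 2.02% | 1.17 | 0.18 |
| 20% vs 2% | 2 | 2.76% | 2.06% | 1.34 | 0.36 |
| 40% vs 3% | 2 | 3.53% | 2.10% | 1.68 | 0.74 |

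*Fixed per-biopsy rate, q = 1%, b = 1:*

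| PAEC | e | P, higher | P, lower | Ratio | Excess per 52 women |
|---|---|---|---|---|---|
| 10% vs 2% | 1 | 1.10% | 1.02% | 1.08 | 0.04 |
| 30% vs 5% | 1 | 1.30% | 1.05% | 1.24 | 0.13 |
| 30% vs 5% | 2 | 1.59% | 1.10% | 1.45 | 0.26 |
| 60% vs 5% | 2 | 2.18% | 1.10% | 1.99 | 0.56 |

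The ratio hardly depends on *q*, but the excess does. In the most extreme row (60% vs 5%, two repeats) it is 1.11 women at q = 2% and 2.65 at q = 5%.

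*Two base looks (b = 2, e = 1).* The ratio falls to 1.09 for 20% vs 2% at q = 1.985%, and to 1.12 for 30% vs 5% at q = 1%.

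*Majority read.* With 0.5% per reader and independence, two of three gives q = 3(0.005)²(0.995) + 0.005³ = 0.0075%. The excess is 0.0007 women per 52 (20% vs 2%, one repeat) to 0.003 (40% vs 3%, two repeats). Readers of the same sample are probably not independent, so the true majority rate could be higher. The ratios stay similar.

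**Exit rule.** If a share *v* of PAEC resolves per repeat, the last-value PAEC rate is s·(1 − v)^e. An assumed 30% at the first biopsy becomes 30% × 0.5 = 15% after one repeat with 50% resolution, or 30% × 0.2 = 6% with 80%.

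**After the fix.** With one look per woman, chosen without regard to PAEC, P = q in both groups and the ratio is 1.00.

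**The case against.** **Other triggers.** A reader might infer that only women with PAEC are re-biopsied. The protocol does not support that: an inadequate sample, one reader more severe than the majority, hyperplasia or malignancy, thickness above 18 mm and suspicious bleeding can each lead to a repeat in any woman. This does not remove the point. A repeat for an inadequate sample replaces a lost look, and a repeat after a non-benign read follows a biopsy already scored non-benign in the all-reads result. Only for thickness and bleeding is the balance between groups unknown.

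**Direction.** A reader might infer a bias against vilaprisan in the group tables. That does not follow. All three groups were planned to receive vilaprisan. Women completing both periods end on vilaprisan in A1 and B1 and on placebo in B2. Women stopped after Treatment Period 1 by the pause end on vilaprisan in A1 and B2 and on placebo in B1. The contrasts computed above are therefore not planned tables. Section 9.6.3.2.6 also says that PAEC features can occur without exposure to the class.

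**Exit.** A reader might call the last-value rule an error. It is not: the protocol wants each woman to leave without a relevant finding, and status at exit answers that. Earlier findings remain in the worst-case tables.

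**Existing safeguards.** By-biopsy percentages avoid the worst-of-several problem, although they give re-biopsied women more weight. SAP 6.1.1 counts women with endometrial monitoring at closeout, but not biopsies per woman or their triggers.

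**Size.** All rates are assumed, the absolute excess is mostly a fraction of a woman, and the planned sample was not reached. The original schedule had biopsies at both end of treatment and follow-up, so two base looks may be the better case for any time point. All this stands and keeps the point modest.

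**Conclusion.** The point holds for the follow-up-phase, any-time-point and exit summaries. There the number of post-treatment biopsies depends partly on PAEC, the worst-case and last-value rules carry that dependence into the results, and SAP 6.4.1.1 plans neither a fixed-look table nor a count of biopsies by trigger.

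The size cannot be computed from the documents. Under the assumptions shown (equal true risk, independent looks, one or two extra biopsies), ratios run from about 1.04 to 2.0. The excess stays below one woman per 52 for per-biopsy rates up to 1%, and at about 2% in all but the most extreme row. It is far smaller for the majority read, on which Protocol 9.6.3.2.4 bases the main evaluation. Error rates, power and the confirmatory tests are not affected. This is an inexpensive improvement to a descriptive safety comparison.

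One matter needs reconciling in any case. Protocol 11.3 sends biopsies taken after the follow-up visit to an addendum outside the study report, while SAP 4.5 makes the safety closeout visit the exit examination. Together they leave unclear which repeats enter the tables.

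**What to change.** In SAP 6.4.1.1:

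1. Add a subject-level table, by treatment group and by last study drug received, using each woman's first adequate post-treatment biopsy (the first at or after last dose minus 7 days, the protocol's own definition of post-treatment). Show PAEC-triggered repeats separately, as resolution.
2. Tabulate biopsies per woman by group and trigger: scheduled, closeout, PAEC repeat, inadequate sample, thickness or bleeding, and follow-up of an abnormal read.
3. Keep the worst-case and exit tables, labelled as worst case and as status after follow-up.
4. Reconcile Protocol 11.3 with SAP 4.5 and state which repeat biopsies enter each table.

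The cost is SAP wording, a trigger flag and one or two extra tables from data already collected. No biopsy is added or removed. A finding seen only on a repeat biopsy will not appear in the new table, but remains in the worst-case table and the listings.

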6.4.1.2 Endometrial thickness

For the analysis of endometrial thickness, the following time intervals will be considered:

- Intervals A (acc to Figure 4–1)
- Intervals C (acc to Figure 4–1)
- "Exit examination" intervals

Number of subjects with ultrasound performed for the time intervals will be presented as well.

Descriptive statistics for change from baseline in endometrial thickness will be provided. In addition, the proportion of subjects with endometrial thickness >18 mm will be investigated. A subgroup analysis by exposure group (i.e., treatment duration \leq 90 days, 91 to 180 days,

etc.) will present the proportion of subjects with endometrial thickness >18 mm and cyst like structure either ovary > 3 cm.

The correlation between endometrial thickness and biopsy results will be studied based on biopsies with endometrial thickness value measured on the day of an endometrial biopsy. The following proportions will be compared between patients with endometrial thickness >18 mm and patients with endometrial thickness ≤ 18 mm (measured by ultrasound):

- Proportion of biopsies with non-benign and benign results in all readers,
- Proportion of biopsies with PAEC present and PAEC not present,
- Proportion of biopsies with extensive cysts present and not present.

Intervals A will be used for this analysis.

6.4.2 Other safety variables

6.4.2.1 Endometrial histology (PAEC)

The analysis of progesterone receptor modulator-associated endometrial changes (PAEC) will be presented together with further results of endometrial histology. A detailed description of the analyses can be found in Section 6.4.1.1.

6.4.2.2 Ovarian cysts

Ovarian cysts will be examined by ultrasound. All scheduled and unscheduled assessments will be considered for the analysis. Three analyses will be performed for ovarian cysts:

- Number of subjects showing cyst like structures with largest diameter >3 cm in the ovary
- Analysis of ovarian cyst episodes (see below for definition)
- Analysis of AEs associated with ovarian cysts

The analysis of *Number of subjects with ovarian cyst like structures* > 3 cm in largest diameter in ovary will be shown by treatment group and by time intervals. Intervals A and Intervals B will be considered. One table will be produced for Intervals A and one table for Intervals B.

For each time interval it will be determined whether an individual subject shows cysts like structures with a largest diameter > 3 cm at least once during that time interval. In addition to the corresponding time intervals, both tables will contain the assessment for the 'Exit examination'.

Frequencies for the type of cyst like structures identified will be included in the table. Type of cyst like structures will be shown as recorded in the eCRF: 'Follicle-like structure', 'Corpus luteum cyst', 'Endometrioma' and 'Other'.

The overall assessment for both ovaries will be displayed, and information about ovary laterality will not be included in the table.

If cyst like structures with diameter > 3 cm are visualized in the ovaries, unscheduled ultrasound examinations should be performed at least every 4 weeks to document the regression or outcome. An *ovarian cyst episode* is defined as the time period from occurrence

of a cyst like structure with diameter > 3 cm until its resolution. Ovarian cyst episodes will only take account of the occurrence of follicle-like structures and corpus luteum cysts. Two different definitions of "resolution" are used in the analysis:

- The subject does not show in the same ovary (left or right) a cyst like structure of the same type,
- The subject does not show in the same ovary (left or right) a cyst like structure of the same type with diameter > 3 cm.

For both definitions, the date of the first observation of the cyst like structure is the *start of the episode*. The date when the cyst like structure appears for the first time as resolved (absence of cyst like structure or cyst like structure with diameter > 3 cm) is considered the *end of the episode*. The length of time between start and end of the episode is the *duration of the episode*.

If the cyst resolution does not occur, then the length of time between the start of the episode and the last observation will be considered the cyst episode duration.

If only the start of the episode is recorded but no follow-up has been performed, then the duration of the episode is unknown.

The analysis will include cysts episodes occurring in both ovaries with no distinction of ovary laterality (left or right). Although the information of ovary laterality will not be displayed in the table, it will be critical to monitor the progression of individual cyst like structures.

The Intervals A and B (acc to Figure 4–1) will be considered. Therefore, two sets of tables will be produced. Ovarian cyst episodes will be assigned to the time interval when the start of the episode occurs.

Two analyses will be produced for ovarian cyst episodes:

- Number of subjects with at least one ovarian cyst episode by time intervals.
- Number of ovarian cyst episodes by time intervals including: i) descriptive statistics of ovarian cyst episode duration, ii) by categorization of the duration by 4-week intervals, and iii) descriptive statistics of largest diameter of the cyst like structure per episode and per time interval.

Two tables will be produced for these two analyses, one for each definition of cyst episode resolution.

The analysis of AEs originating from ovarian cysts will include AEs identified by the Bayer MedDRA query (BMQ) for 'Benign ovarian cyst and associated complications' [V21], which include the preferred terms (PTs): Haemorrhagic ovarian cyst, Ovarian cyst, Ovarian cyst ruptured and Ovarian cyst torsion.

The table will show number of subjects with AEs, non-serious AEs and serious AEs (SAEs). For each one of these AE categories the table will include severity, whether the AE led to drug withdrawal (if applicable) and AE duration. In addition, SAEs will include the reason for being classified as serious as recorded in the eCRF.

The analysis will be done for pre-treatment AEs, TEAEs and post-treatment AEs. Pretreatment and post-treatment AEs will be shown by treatment group (including pooled group A1+B2) only. TEAEs will be shown by treatment group for TP1, TP2 and overall, and additionally they will be shown by study drug. AEs with onset during a treatment period or up to 8 days after last study drug intake in any treatment period will be considered 'on-

treatment'. AEs with onset after date of last study drug intake in any treatment period + 8 days and before the start of the next treatment period will be considered 'off-treatment'. The summary table for TEAEs will be presented by overall AEs, on-treatment AEs and off-treatment AEs.

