### **9.7.5 Monitoring of ovarian cysts**

If cyst like structures  $>30$  mm without suspicious appearance (ie, functional ovarian cysts) are visualized in the ovaries, unscheduled ultrasound examinations should be performed every 4 weeks or more frequently, if required due to symptoms, to document the regression/outcome.

If the subject demonstrates menstrual cyclicity, the ultrasound should be performed after menstruation as soon as possible, preferably in the early follicular phase. The monitoring will be continued until resolution, ie, until cyst can no longer be distinguished from functional follicles. If the cysts persist after 3 months or grow, decision on further treatment should be made according to local medical practice.

In the event of cyst like structures with suspicious appearance, further procedures should be performed according to local medical practice.

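### Ovarian cyst episodes not seen to resolve are tabulated as if they ended at the last scan, which shortens the duration displays in SAP 6.4.2.2

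*SAP*

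**What the plan says.** SAP 6.4.2.2 runs an episode from the first observation of a cyst-like structure larger than 3 cm to its resolution, under two alternative definitions of resolution. Three duration rules follow:

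- Resolved: "The length of time between start and end of the episode is the" duration, the end being the first scan that shows resolution.
- Not resolved: "the length of time between the start of the episode and the last observation will be considered the cyst episode duration".
- No repeat scan: "If only the start of the episode is recorded but no follow-up has been performed, then the duration of the episode is unknown".

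The planned output, by time interval and once per resolution definition, includes "descriptive statistics of ovarian cyst episode duration, ii) by categorization of the duration by 4-week intervals". The text specifies no censoring indicator, no count of unresolved episodes and no split between resolved and unresolved.

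On follow-up, the SAP says that "unscheduled ultrasound examinations should be performed at least every 4 weeks to document the regression or outcome". Protocol 9.7.5 goes further: "The monitoring will be continued until resolution, ie, until cyst can no longer be distinguished from functional follicles". It also foresees persistence: "If the cysts persist after 3 months or grow, decision on further treatment should be made according to local medical practice".

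**The concern.** For an episode not seen to resolve, the time to the last scan is only a lower bound on its duration. The SAP gives that lower bound the same name as a completed duration and summarises the two together. Pooling is not stated in so many words, but it follows from one variable with no split. A cyst still larger than 3 cm at its only repeat scan, 4 weeks after detection, falls in the same 4-week category as a cyst that had gone by that scan. For a persistent cyst, the shorter the follow-up, the shorter the tabulated episode.

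The SAP handles the same problem properly elsewhere. Time to start of bleeding (6.2.3.2) is censored at the last available diary date. Time to ALT above 3×ULN (6.4.2.8) uses Kaplan-Meier with censoring. The onset endpoints (6.2.2) have detailed censoring rules. So this is a stated rule that treats censored times as events, not a detail left open.

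At stake is a descriptive safety display that errs in the reassuring direction. Some open episodes are also likely at the first analysis, because SAP 4.4 takes cleaned data to 31 DEC 2019 plus whatever else is available, ahead of the final analysis.

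**Working it through.** The plan gives no figure for cyst duration, number of episodes or share unresolved, so there is nothing to reproduce. The steps below fix the direction and illustrate the size. T is the true duration, C the end of observation, m the assumed mean of T. The 4-week scan spacing comes from SAP 6.4.2.2; every other input is an assumption.

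**1. Direction.** The SAP records min(T, C). If T > C the record is C, which is below T. Example: 8 of 10 cysts have gone at 4 weeks and 2 are still present at their only repeat scan at 4 weeks. The SAP mean is (8×4 + 2×4)/10 = 4.0 weeks, the same as if all ten had resolved.

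**2. Continuous time.** If T is exponential and C independent, E[min(T, C)]/E[T] = P(T ≤ C), the share resolved. With 10, 20, 30 or 40% unresolved, the recorded mean is 90, 80, 70 or 60% of the true mean.

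**3. Long follow-up, 4-weekly scans to 36 weeks.** Let q = exp(−4/m). Mean time to the detecting scan without censoring is 4/(1−q). Under the SAP rule it is 4(1−q⁹)/(1−q), so the relative shortfall is q⁹ = exp(−36/m).

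- m = 8: q = 0.6065, q⁹ = 0.0111; 10.05 against 10.17 weeks, low by 1.1%.
- m = 12: q = 0.7165, q⁹ = 0.0498; 13.4 against 14.1 weeks, low by 5.0%.
- m = 4: q⁹ = exp(−9), about 0.0001; negligible.

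**4. Earlier loss of follow-up.** Simulation of 400,000 episodes per scenario. T is exponential and resolution is recorded at the next 4-weekly scan. C is exponential and independent, with its rate set so that the chance that T > C is 10 to 40%; the last scan is the last 4-weekly scan before C. Episodes with no repeat scan are dropped, as in the SAP. The table shows the 10% and 40% scenarios; unresolved is among episodes with at least one repeat scan.

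| m (weeks) | Chance T > C | Unresolved | SAP mean | Mean without censoring | Low by | >12 weeks: SAP | >12 weeks: no censoring | >12 weeks: Kaplan-Meier |
|---|---|---|---|---|---|---|---|---|
| 4 | 10% | 5.7% | 5.95 | 6.32 | 6% | 3.5% | 4.9% | 4.9% |
| 4 | 40% | 22.1% | 4.94 | 6.33 | 22% | 0.7% | 5.0% | 4.9% |
| 8 | 10% | 7.7% | 9.40 | 10.18 | 8% | 19.0% | 22.4% | 22.7% |
| 8 | 40% | 30.3% | 7.08 | 10.15 | 30% | 8.2% | 22.3% | 22.3% |
| 12 | 10% | 8.3% | 12.90 | 14.07 | 8% | 32.8% | 36.6% | 36.4% |
| 12 | 40% | 33.4% | 9.38 | 14.08 | 33% | 18.9% | 36.7% | 36.7% |

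Across all twelve scenarios (10, 20, 30 and 40% at each m), the SAP-rule median equalled the Kaplan-Meier median in six and was one scan interval (4 weeks) lower in six. Kaplan-Meier recovers the share above 12 weeks here because censoring was made independent of duration.

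**The case against.** The strongest reply is that follow-up was planned to be long, so few episodes should be cut short. Protocol 9.7.5 asks for monitoring until resolution. SAP 6.4.2.2 uses all scheduled and unscheduled scans. The safety closeout visit (Protocol Table 9–1 and 9.6.3.6) includes an ultrasound of the ovaries and is requested from every treated subject. A subject who began a 12-week period just before Amendment 4 (11 DEC 2018) would have finished about 5 March 2019. From then to Version 5.0 (20 NOV 2019) is 260 days, or 37 weeks, so a closeout scan falls late. This stands, and it is why step 3 gives a bias of only a few percent. It does not cover subjects who declined closeout or left with a cyst present, whose number the documents do not give.

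Three further replies also stand. The listed safety variable is ovarian cysts by number and size (Protocol 10.3.1.6, SAP 6.4); duration is a supplementary display. Both tables of subjects with cysts include the exit examination, which shows who left with a structure larger than 3 cm, and all observations are listed. Table layouts sit in a separate specification (SAP 4.1), so a row for unresolved episodes is absent from the SAP text but not excluded by it.

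Readers might infer more than the documents support:

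- **That cyst persistence is understated throughout the report.** Subject counts and exit status do not use the duration rule.
- **That long episodes would vanish from the table.** This happens only if every last scan is assumed to fall within 12 weeks, in which case it is true by construction; the planned follow-up says otherwise.
- **That the bias differs between arms.** Nothing in the documents shows this.
- **That the table fails to measure a 3-month endpoint.** In Protocol 9.7.5 the 3 months is a prompt to sites, not an analysis threshold.

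**Conclusion.** The point holds for the episode-duration statistics and the 4-week categories only. Their direction of error is certain whenever an episode is unresolved at a last scan after the start of the episode: tabulated durations are too short relative to the same scan-based duration with censoring. The claim is not about biological duration, since recording resolution at the detecting scan lengthens an episode and late first detection shortens it.

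The size cannot be computed from the documents. It may be small if monitoring until resolution was achieved, and a third of the mean at the severe end of the ranges assumed above; those figures rest on exponential durations, 4-weekly scans and independent censoring. All safety analyses are descriptive (SAP 6.4), so no test or confirmatory conclusion changes. The change is still worth making, because the rule is wrong as written and the correction is cheap.

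**What to change.** Amend SAP 6.4.2.2, under both resolution definitions, to:

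- flag episodes not seen to resolve as right-censored at the last observation, and drop the rule that calls this time the duration;
- report the numbers of episodes resolved, unresolved at last observation (with their follow-up time) and without any follow-up scan;
- show the 4-week categories with unresolved episodes in a separate row;
- give Kaplan-Meier estimates of duration where episode numbers allow. The planned 156 subjects were not reached (Protocol 10.4), so in sparse cells the counts may have to suffice.

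While editing, reconcile the parenthesis that describes a resolved cyst. As it reads, it includes a structure with diameter above 3 cm, which contradicts the second resolution definition.

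Cost: SAP wording, slightly more table work for each resolution definition, and longer reported durations. No new data are needed.
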